- The M9241 immunocytokine is composed of 2 IL-12 heterodimers, each fused to one of the H-chains of the NHS76 antibody, which has affinity for both single- and double-stranded DNA. M9241 targets delivery of IL12, a proinflammatory cytokine that has been shown anti-tumor activity including objective responses in phase I clinical trials, to regions of tumor necrosis where DNA has become exposed, e.g. after radiation therapy.
- We hypothesize that released neo-epitopes upon increased DNA damage induced by radiation therapy together with the local proinflammatory action of M9241 will complement the anti-tumor activity of M7824 in locally advanced pancreas cancer.

Objectives:

- To determine the safety and tolerability and the recommended phase 2 dose (RP2D) of M7824 and M9241 in combination with SBRT as neoadjuvant / perioperative treatment in subjects with pancreas cancer.
- To determine a preliminary estimate of efficacy as best overall response (BOR) according to RECIST 1.1 of M7824 and M9241 in combination with SBRT as neoadjuvant / perioperative treatment in subjects with locally advanced pancreas cancer.

Eligibility:

- Histologically or cytologically proven pancreatic adenocarcinoma.
- Patient must be eligible to undergo stereotactic body radiation therapy (SBRT) (Cohorts 2-3).

Abbreviated Title: M7824, M9241 and SBRT

Version date: 11/10/2021

- Patients must have measurable disease.
- Age ≥ 18 years

Design:

- This is an open label Phase I/II trial. During phase I the safety and tolerability of M7824 and M9241 will be evaluated and recommended Phase II dose (RP2D) of M7824 and M9241 in combination with SBRT will be estimated. During phase II efficacy of the M7824 and M9241 in combination with SBRT will be examined.
- Patients will receive treatment in cycles consisting of 28 days (with exception of additional administer of M7824 alone in Phase IA).
- Treatment will continue until unacceptable toxicity or disease progression.
- If during treatment patient become candidate for curative surgery, treatment will be stopped and can be restarted after surgery in case if surgical exploration does not result in the successful removal of the tumor.

TABLE OF CONTENTS

PRÉCIS	2
TABLE OF CONTENTS	4
STATEMENT OF COMPLIANCE	10
1 INTRODUCTION	10
1.1 Study Objectives:	10
1.1.1 Primary Objectives:	10
1.1.2 Secondary Objectives:	10
1.1.3 Exploratory Objectives:	10
1.2 Background and Rationale	11

The protocol, informed consent form(s), recruitment materials, and all participant materials will be submitted to the Institutional Review Board (IRB) for review and approval. Approval of both the protocol and the consent form must be obtained before any participant is enrolled. Any amendment to the protocol will require review and approval by the IRB before the changes are implemented to the study. In addition, all changes to the consent form will be IRB-approved; an IRB determination will be made regarding whether a new consent needs to be obtained from participants who provided consent, using a previously approved consent form

1 INTRODUCTION

1.1 STUDY OBJECTIVES:

1.1.1 Primary Objectives:

- To determine the safety and tolerability and the recommended phase 2 dose (RP2D) of M7824 and M9241 in combination with SBRT as neoadjuvant / perioperative treatment in subjects with pancreas cancer.
- To determine a preliminary estimate of efficacy as best overall response (BOR) according to RECIST 1.1 of M7824 and M9241 in combination with SBRT as neoadjuvant / perioperative treatment in subjects with locally advanced pancreas cancer.

1.1.2 Secondary Objectives:

- To assess overall survival (OS) in patients after completion of RT in combination with M9241 and M7824.
- To assess progression-free survival (PFS) for all participants.
- To assess progression-free survival (PFS) for participants who did not undergo surgical resection.
- To determine fraction of patients with LAPC who are able to undergo surgical resection after M7824 and M9241 in combination with SBRT treatment.
- For patients who underwent surgical resection after M7824 and M9241 in combination with SBRT treatment:
 - To determine time-to-recurrence of the disease
 - To determine complete pathological response rate(s)

1.1.3 Exploratory Objectives:

- To determine ADA profile of M7824 in combination with M9241.

- To determine the PK of M7824 in combination with M9241.
- To evaluate serum cytokines and tumor necrosis factor (TNF) levels pre-treatment and on-treatment.
- To correlate the tumoral immune infiltrate via IHC with clinical outcome.
- To evaluate impact of genomic profile of advanced pancreatic cancers on clinical response to M7824 and M9241 in combination with SBRT.
- To correlate circulating free tumor DNA (ctDNA) levels with clinical course of pancreatic cancer patients treated with M7824 and M9241 in combination with SBRT.
- To measure subjective Health-related Quality of Life (HRQoL) affecting disease-specific symptoms and treatment-related concerns pre-treatment and on-study and compare HRQoL scores with historical controls of other Quality of Life (QoL) interventions in advanced pancreas cancer patients.
- To evaluate the impact of M7824 in combination with M9241 on tumoral perfusion measured by perfusion-weight Dynamic Contrast-enhanced (DCE) Magnetic Resonance Imaging (DCE-MRI).

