
 • Bleeding adverse events are considered an important identified risk for M7824. • In general, mild and moderate mucosal bleedings resolve without discontinuation of treatment. • These events may include, but are not limited to the following: 
 ○ Epistaxis ○ Hemoptysis ○ Gingival bleeding ○ Hematuria 	
Non-tumor Bleeding	
Grading	Management
Grade 2	
 • If resolves to Grade ≤ 1 by the day before the next infusion, study intervention may be continued. • If not resolved to Grade ≤ 1 by the day before the next infusion, but is manageable and /or not clinically relevant, consult Medical Monitor to assess if clinically reasonable to administer the following infusion.
Grade 3	
 • Permanently discontinue treatment unless an alternative explanation can be identified (such as concomitant use of antithrombotic agents, traumatic events, etc.) • In case of alternative explanations, hold study treatment until the event recovers to Grade ≤ 1

Grade 4	
 Treatment must be permanently discontinued if no alternative explanation is identified.
Tumor Bleeding	
Grade \geq 2	
 Study treatment must be held till the event recovers to Grade \leq 1 Permanently discontinue treatment if the Investigator considers the participant to be at risk for additional severe bleeding.

Table 12: Impaired Wound Healing

 Impaired wound healing is considered important potential risk for M7824 Management should be discussed with Medical Monitor for participants requiring surgery on study. It is recommended to hold study intervention for approximately 4 weeks post major surgery for observation. Post-operative wound healing should be closely monitored

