3.5.3 Treatment pauses for surgery

Surgery is not part of this protocol and will be done as standard of care procedure with enrollment of patient to another surgical protocol at the NIH Clinical Center or at home institution.

If during the treatment patient's tumors become resectable per standard of care, M7824 and/or M9241 will be stopped at least 5 days prior to the scheduled date of surgery.

If surgery performed outside NIH, we will ask patients to provide the outside surgical pathology report for determination of resection status (R0, R1, R2) and tumor sample from this surgery for research.

If surgical exploration does not result in a successful removal of the tumor as defined below:

- R0: closest tumor ≥ 1 mm from surgical resection margin
- R1: tumor within < 1 mm of surgical resection margin

- R2: involvement of surgical resection margin with tumor (incomplete tumor clearance)
- “open and close”

treatment with M7824 and M9241 will resume 6-8 weeks after surgery when patient recovers. SBRT will not be repeated.

If surgical exploration results in a successful removal of the tumor, patient will be taken off study treatment.

Before post-surgery re-treatment with M7824 and M9241, Day 1 the following tests and examinations must be performed to evaluate safety of re-treatment and estimate baseline for tumor evaluations:

Within 28 days:

- CT/MRI of chest, abdomen and pelvis;
- Research Quality of Life assessment (subject-reported outcomes / symptom severity assessments the 4th version of the ‘Functional Assessment of Cancer Therapy with the hepatobiliary and pancreatic specific module ([Appendix C](#)). (For English speaking subjects only)

Within 3 days:

- Physical examination, including weight, vital signs, EKG, and ECOG performance status;
- Adverse event and concomitant medications;
- Laboratory evaluation:
 - Hematological profile: CBC with differential and platelet count;
 - Biochemical profile: Acute care panel (that includes sodium, potassium, BUN, creatinine), Hepatic panel (that includes AST, ALT, total bilirubin), Mineral panel (that includes calcium, phosphorus, albumin, and magnesium), and uric acid;
 - CEA, CA19-9, CA-125
 - T4, TSH
 - Amylase/ lipase
 - Serum or urine pregnancy test for female participants of childbearing age (in the absence of prior hysterectomy)
 - Urinalysis.

Research blood will not be collected during post-surgery treatment

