6 DATA COLLECTION AND EVALUATION

6.1 DATA COLLECTION

The PI will be responsible for overseeing entry of data into an in-house password protected electronic system (C3D) and Labmatrix ensuring data accuracy, consistency and timeliness. The principal investigator, associate investigators/research nurses and/or data manager will assist with the data management efforts. Primary and final analyzed data will have identifiers so that research data can be attributed to an individual human subject participant.

All adverse events, including clinically significant abnormal findings on laboratory evaluations, regardless of severity, will be followed until return to baseline or stabilization of event.

Document AEs from the administration of the first study intervention through 28 days after the last study agent (s) is administered. Beyond 28 days after the last intervention, only adverse events which are serious and related to the study intervention need to be recorded.

An abnormal laboratory value will be recorded in the database as an AE only if the laboratory abnormality is characterized by any of the following:

- Results in discontinuation from the study
- Is associated with clinical signs or symptoms
- Requires treatment or any other therapeutic intervention
- Is associated with death or another serious adverse event, including hospitalization.
- Is judged by the Investigator to be of significant clinical impact

- If any abnormal laboratory result is considered clinically significant, the investigator will provide details about the action taken with respect to the test drug and about the patient's outcome.

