6.1.3 Concomitant Medications and Therapies

All concomitant medications taken by the subject during the trial, from the date of signature of informed consent are to be recorded in the appropriate section of the eCRF, noting the name, dose, duration and indication of each drug. Nondrug interventions should also be recorded in the eCRF.

The following outcome criteria will be captured if surgery performed while patient is on study:

- Number of patients explored
- Number of patients to undergo resection
- Number of R0, R1, and R2 resection

End of study procedures: Data will be stored according to HHS, FDA regulations and NIH Intramural Records Retention Schedule as applicable.

Loss or destruction of data: Should we become aware that a major breach in our plan to protect subject confidentiality and trial data has occurred, this will be reported expeditiously per requirements in section [7.2.1](#).

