10 STATISTICAL CONSIDERATIONS

10.1 STATISTICAL HYPOTHESIS

10.1.1 Primary endpoints:

- To determine the safety and tolerability and the recommended phase 2 dose (RP2D) of M7824 and M9241 in combination with SBRT as neoadjuvant / perioperative treatment in subjects with pancreas cancer:
 - number, severity, and duration of treatment-related AEs for the combination treatment of M7824 and M9241 administered in combination with a 5-day course of SBRT according to CTCAE v5.0
 - rate of completion of neoadjuvant SBRT courses when given with M7824 and M9241.
- To determine a preliminary estimate of efficacy as best overall response (BOR) according to RECIST 1.1 of M7824 and M9241 in combination with SBRT as neoadjuvant / perioperative treatment in subjects with locally advanced pancreas cancer will be measured by
 - Best Overall Response (BOR) according to RECIST 1.1

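### Perioperative safety is a primary objective, but full adverse-event recording is anchored to the last drug dose and covers at most 23 days after a resection

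*Combined protocol and SAP*

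**What the plan says.** Section 1.1.1 sets the first primary objective as safety, tolerability and the recommended phase 2 dose "of M7824 and M9241 in combination with SBRT as neoadjuvant / perioperative treatment in subjects with pancreas cancer". Section 10.1.1 measures it by "number, severity, and duration of treatment-related AEs for the combination treatment of M7824 and M9241", plus the rate of SBRT completion.

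The recording rule is in section 6.1: "Document AEs from the administration of the first study intervention through 28 days after the last study agent (s) is administered". It continues: "Beyond 28 days after the last intervention, only adverse events which are serious and related to the study intervention need to be recorded". AEs already recorded are followed to baseline or stabilization.

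On surgery, section 3.5.3 states that "M7824 and/or M9241 will be stopped at least 5 days prior to the scheduled date of surgery". After successful removal the patient leaves study treatment. After an unsuccessful exploration, "treatment with M7824 and M9241 will resume 6-8 weeks after surgery when patient recovers", with an AE review within 3 days before re-treatment.

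Table 12 in section 3.4.1 states: "Impaired wound healing is considered important potential risk for M7824". It recommends a drug hold of about 4 weeks after major surgery for observation, with close monitoring of the wound. The surgical outcomes listed in section 6.1.3 are the number explored, "Number of patients to undergo resection", and the R0, R1 and R2 counts. The list has no complication item.

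**The concern.** An objective that includes perioperative safety needs a record of what happens after the operation. Here the recording clock starts from the last dose, so a longer interval between drug and surgery leaves fewer post-operative days fully recorded. The safety visit in the study calendar (section 3.8, note 14) is also timed from the last dose, and no visit is timed from surgery.

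The events at stake are wound, anastomotic and bleeding complications. The protocol itself names impaired wound healing as a potential risk of M7824. Such an event, if non-serious or judged unrelated, need not be recorded once the window closes. In a single-arm trial, relatedness is a case-by-case judgement. A slow-healing wound after pancreatic surgery could reasonably be attributed either to the surgery or to the drug, and an unrecorded event cannot be reassessed later.

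**Working it through.** **Inputs.** Full recording ends 28 days after the last agent (section 6.1). The gap g from last dose to surgery is at least 5 days, with no stated maximum (section 3.5.3). Drug resumes 42-56 days after surgery, if at all (section 3.5.3). The safety visit is 28 ± 5 days after the last dose (section 3.8, note 14). The plan states no figure for post-operative coverage, so there is none to reproduce.

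**Patient not restarted on drug** (tumor removed, or failed exploration without resumption). Fully recorded post-operative days = max(0, 28 - g).

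| Gap g (days) | Days of full recording after surgery |
|---|---|
| 5 (minimum allowed) | 28 - 5 = 23 |
| 7 | 28 - 7 = 21 |
| 14 | 28 - 14 = 14 |
| 21 | 28 - 21 = 7 |
| 28 or more | 0 |

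Gaps above 5 are illustrations; the protocol neither sets nor predicts them.

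**Against Table 12.** Four weeks is 28 days. Since g is at least 5, 28 - g is always below 28. Full recording therefore ends before that observation period does, at every permitted gap. The shortfall is at least 5 days.

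**Safety visit.** At g = 5 it falls between post-operative day 28 - 5 - 5 = 18 and day 28 + 5 - 5 = 28. A longer gap moves it earlier.

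**Patient who resumes drug.** The last dose is now post-operative. With only one further dosing day, the window ends at day 42 + 28 = 70 to day 56 + 28 = 84, and later with more doses. The pause is covered only in retrospect: until drug restarts, the window may appear to have closed by day 23.

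**What is lost after the window closes** (patient not restarted on drug).

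| AE type | Recorded after the window? |
|---|---|
| Serious and related | Yes, no end date given |
| Already recorded, still ongoing | Followed to baseline or stabilization |
| Non-serious, related | Need not be |
| Judged unrelated, any seriousness | Need not be |

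**How many patients.** Section 1.2.1 cites resection rates of 7-19% for unresectable and 40-60% for borderline disease under existing radiotherapy regimens. Taking these as assumptions for 25 phase II patients: 25 × 0.07 = 1.75 and 25 × 0.19 = 4.75 if all are unresectable; 25 × 0.40 = 10 and 25 × 0.60 = 15 if all are borderline. That is about 2 to 15 resections, plus any failed explorations. With 0 events in 10 operated patients, the exact two-sided 95% upper limit is 1 - 0.025^(1/10) = 0.308, or 31%. Numbers this small leave little room to lose events.

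**The case against.** A reader might infer that AE capture stops altogether at day 23. The documents do not say so. Serious related AEs are recorded later with no end date, recorded AEs are followed to stabilization, note 14 of the study calendar follows later drug-related SAEs, and the calendar marks AEs at long-term follow-up. Hospitalization or its prolongation makes an event serious (section 8.1.2), and section 8.1.5 defines related as a reasonable possibility of causation. A major wound or bleeding complication could therefore still be recorded. That surgical complications would usually be called unrelated is an assumption no section supports. The narrower statement stands: if judged unrelated after the window, they need not be recorded.

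A reader might also infer that the RP2D is compromised. It is not. It rests on DLTs over 4 weeks in phase IB, after a 6-week DLT period in phase IA (sections 3.1.1 and 3.1.2), and the first planned on-treatment imaging is at Cycle 3 Day 15.

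Nor is a planned comparison biased. Section 10.4 contains no safety comparison of operated patients, and section 10.4.2 confines the primary safety report to the de-escalation portion. The unequal windows follow from whether drug resumes, not from the surgical result as such.

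Finally, surgery is expressly outside the protocol, and Table 12 already asks for close wound monitoring. Both points are fair, but Table 12 is clinical guidance and does not extend the recording period. Resection fraction, pathologic response and time to recurrence are endpoints (section 10.1.2), so the trial already relies on the surgery for efficacy.

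**Conclusion.** The concern holds as a mismatch between the scope of the primary safety objective and the recording rule in section 6.1. Without resumption of drug, all-grade, all-cause recording covers at most 23 post-operative days, and none if surgery comes 28 or more days after the last dose. With resumption it reaches at least day 70-84. The 23-day bound follows from the stated rules alone. The smaller figures depend on assumed gaps, and the 70-84 figure assumes a single post-operative dosing day.

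The loss is partial: non-serious related AEs, which belong to the primary endpoint, and AEs judged unrelated, including complications attributed to surgery. Dose selection is unaffected, and the documents do not support a claim that the primary safety result as a whole is invalid. This is an inexpensive improvement worth making, not a fatal defect.

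**What to change.** In section 6.1, add that for every participant explored or resected after protocol treatment, all AEs are recorded, whatever their seriousness or attribution, through one fixed window from the date of surgery. Thirty days is an example; what matters is that the window is the same whether or not drug resumes. In section 10.4.4, add the number and proportion of operated patients, in both phases, with a Grade 3 or higher post-operative AE in that window, with a 95% CI. Deaths should already be available from survival follow-up.

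Before reporting by surgical outcome, reconcile section 3.5.3, which lists R0 together with R1, R2 and open-and-close under unsuccessful removal. As written, the groups cannot be cleanly assigned.

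If the window is not added, narrow the perioperative wording of the safety objective in sections 1.1.1, 10.1.1 and 10.4.2 to what the recording rule supports.

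The cost is protocol wording plus a records review or phone contact for each operated patient, about 2 to 15 resections under the rates assumed above plus any failed explorations. Patients operated on at outside institutions will take more effort, although the plan already requests their surgical pathology reports. No treatment rule changes.

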1.2 BACKGROUND AND RATIONALE

Rationale for this study is provided by available preclinical and clinical evidence of the individual mono-immunotherapy components:

- TGF β blockade and PD-L1 inhibition, --- by M7824
- local increase in IL-12 function, --- by M9241, and
- enhanced anti-tumor immunogenicity, --- by radiation therapy (RT)

which synergize / cooperate treatment effect when combined:

- cooperation of PD-L1 checkpoint inhibition with RT
- cooperation of TGF β blockade with RT
- IL-12 immunotherapy (M9241) in combination with RT
- IL-12 immunocytokine therapy (M9241) in combination with TGF β - and PD-L1 inhibition (M7824).

1.2.1 Neoadjuvant therapy for locally advanced pancreas cancer (LAPC)

Pancreatic cancer is a life-threatening disease with a dismal outcome. In 2016, about 48,960 people (24,840 men and 24,120 women) were diagnosed with pancreatic cancer, and 40,560 people (20,710 men and 19,850 women) are estimated to have died of pancreatic cancer.[1] AACR estimates deaths due to pancreas cancer to rank 2nd among all cancer-related deaths in the U.S. by 2030.[2] At time of diagnosis, fewer than 10% of newly diagnosed pancreatic cancer patients present with resectable disease (patients who can undergo surgery; stage I - IIA) and patients able to undergo a margin-negative surgical resection (R0) are reported to have the most favorable outcome achieving 5-year survival rates of 25 – 30% (Figure 1).

[figure not shown]

Figure 1: Percent patients at different AJCC stages at time of initial diagnosis of pancreas cancer. Left: per 7th edition of American Joint Commission of Cancer, AJCC more than 6,000 pancreas cancer patients presenting between 2000 and 2005 to Memorial Sloan-Kettering Cancer Center, NY, and their corresponding 5-year survival rates (right) from MSKCC Pancreatic Cancer Registry.

Approximately 50 to 60 % of patients at time of diagnosis have metastatic disease (stage IV).[3] The rest (one third) of all patients with pancreas cancer have disease that is locally advanced because of local interface or invasion of adjacent structures.[4-6] While ultimately a continuum of disease progression LAPC is subdivided into borderline resectable pancreas cancer characterized by a higher risk of a margin positive surgical resection due to one, or more, interface(s) of the tumor with a mesenteric structure and unresectable, locally invasive disease.[5, 7] There are no commonly agreed criteria of borderline resectable pancreas cancer, different organizations have published slight variations of primarily radiographic criteria which are listed in [Appendix A](#).

The primary goal of neoadjuvant therapy in LAPC is, among tumor control and extension of survival, the conversion to resectable disease achieving a R0 resection.[4] Some series have reported for patients with initially borderline resectable pancreas cancer who after neoadjuvant therapy were able to undergo a margin-negative surgical resection of their tumor similar outcomes like for patients with initially resectable disease.[4, 6, 8, 9] However, even after multimodality therapy that includes surgical resection, 5-year overall survival only reached 25 – 30% with an ongoing risk of systemic and locoregional disease recurrence speaking to the systemic nature of the disease and making pancreas cancer, even in its early stages, a near incurable condition.[4, 7, 9]

Patients unable to undergo margin-negative resection have a poor outcome frequently similar to patients with stage IV disease and have poor quality of life indices due to challenging palliation of gastric outlet, biliary duct obstruction, or neuropathic pain due to local tumor progression.[4] Currently used neoadjuvant RT treatment regimens result in only about 40 – 60% of patients with borderline resectable pancreas cancer to undergo surgical resection and in unresectable LAPC patient conversion are even lower, with only 7% - 19% being able to undergo resection which is increased to 29% with the use of the most involved and toxic combination of triple FOLFIRINOX chemotherapy in combination with RT in highly selected patients.[5, 6, 10] [Figure 2](#) shows the flow diagram and outcome differences between all locally advanced pancreas cancer patients (intent-to-treat), outcome of patients who were able to undergo surgical resection, and patients who could not undergo surgery of one of the first sentinel series on the use of neoadjuvant therapy using gemcitabine-based chemoradiation therapy.[9]

[figure not shown]

Figure 2: MDACC experience of preoperative gemcitabine-based chemoradiation (EBRT) for patients with potentially resectable (borderline) adenocarcinoma of the pancreatic head. Flowchart of all 86 patients on the left, survival curve for all 86 patients and survival curves for the patients who underwent pancreaticoduodenectomy (PD; n=64) versus those who did not undergo PD (n=22). The median overall survival for all patients (intent-to-treat) was 22.7 months, for the resected patients 34 months, and for patients not taken to surgery 7 months.[9]

Thus, the primary goal of neoadjuvant therapy in LAPC is, among tumor control and extension of survival, the conversion to resectable disease achieving a R0 resection. Neoadjuvant therapy provides the theoretical advantages over standard adjuvant therapy including

- treatment of distant micro metastasis
- assessment of tumor response to treatment, and
- better triaging and selection of patients for surgical resection (summarized in [11]).

2016 American Society of Clinical Oncology (ASCO) Clinical Practice Guidelines on locally advanced pancreas cancer (LAPC) recommend ‘Initial systemic therapy with combination regimens is recommended for most patients who meet the following criteria: Eastern Cooperative Oncology Group performance status (ECOG PS) 0 or 1, a favorable comorbidity profile, and patient preference and a support system for aggressive medical therapy.[5] There is no clear evidence to support one regimen over another, and physicians may offer therapy on the basis of extrapolation from data derived from studies in the metastatic setting. For many patients, induction chemotherapy may be offered up front, followed by radiation therapy (CRT), on the basis of patient and physician preference.[5, 12]

If there is an insufficient response to initial induction chemotherapy, which is not uncommonly difficult to judge due to the inability of current radiologic criteria to confidently discriminate between tumor tissue, fibrous tissue without tumor, or fibrous tissue with tumor nests, or if there

is local tumor extension without the development of metastasis after induction chemotherapy, RT may be offered to patients who meet criteria with regard to their performance status, organ function, and preference.[4, 5] Overall, patients with locally advanced pancreas who receive neoadjuvant therapy receive in 98% of cases some form of systemic chemotherapy and in up to 94% RT although the rates for RT administration have recently dropped due to the introduction of oxaliplatin and gem/abraxane-containing chemotherapy regimens into the neoadjuvant setting.[4] RT, like in the proposed study, is generally given either as

- external beam radiation therapy (EBRT) delivering a total dose of 50 – 54 Gy in daily fractions of 1.7 – 3Gy over 4 to 8 weeks, or less frequently with less data available, as
- stereotactic radiation therapy (SBRT) using an abbreviated schedule delivering 5 – 6.6 Gy in 5 session.[5, 6, 12]) (please see Section 1.2.7.)

RT is combined with a chemo sensitizing agent which is either oral capecitabine (oral 5-FU pro-drug; 830mg/m² PO twice daily) or gemcitabine (300mg/m² weekly; therapeutic dose 1,000mg/m²) with despite direct comparison in a radio-chemotherapy (RCT) no clear superiority in efficacy of one over the other.[13] For this study on the days of SBRT 830mg/m² capecitabine twice daily by mouth is given.

Figure 3 provides a flow chart of summary of treatment algorithm of pancreas cancer aligned with ASCO 2016 Practice Guidelines. While the algorithm lists specific chemotherapy regimens in the management of LAPC patients who undergo neoadjuvant treatment, there is currently no consensus that one is superior to the other (FOLFIRINOX vs gemcitabine-based regimens including gem/abraxane) and ASCO Guidelines suggest an individual-based decision making.

[figure not shown]

Figure 3: Overview of currently practiced treatment algorithm for patients diagnosed with pancreas cancer. Please note that there is currently no level I recommendation of type of 1st vs 2nd line chemotherapy in the metastatic setting, or chemotherapy regimens used in the neoadjuvant treatment of LAPC.

Overall, there is a medical need to improve current neoadjuvant treatment of LAPC, ideally with a combination of agents which improves both local response rates as well as long term control of undetected micro metastasis, the to-date most common cause of death in LAPC and pancreas cancer patients in general.

